13.1 Waiver of Documentation

Screening Waiver of Documentation

Check if VA related Y

a) Describe the informed consent process. Include the following.

- Who is obtaining consent? (The person obtaining consent must be knowledgeable about the study.)
- When and where will consent be obtained?
- How much time will be devoted to consent discussion?
- Will these periods provide sufficient opportunity for the participant to consider whether or not to participate and sign the written consent?
- What steps are you taking to minimize the possibility of coercion and undue influence?
- If consent relates to children and if you have a reason for only one parent signing, provide that rationale for IRB consideration.

Qualified research personnel will conduct this screen to determine basic eligibility. We believe it is an excessive burden on the potential participant to require participants to complete the entire informed consent to conduct this brief screen for study eligibility. It will be administered prior to obtaining written informed consent, but after the potential participants have already expressed interest and willingness to provide study personnel to contact them.

b) What is the Procedure to assess understanding of the information contained in the consent? How will the information be provided to participants if they do not understand English or if they have a hearing impairment? See HRPP Chapter12.2 for guidance.

The purpose of the screening interview is given in the script preceding screening. Participant oral assent will be obtained for this screening interview. VA waiver of HIPAA authorization for recruitment has also been included in the protocol.

c) What steps are you taking to determine that potential participants have the capacity to participate in the decision-making process? If your study may enroll adults who are unable to consent, describe (i) how you will assess the capacity to consent, (ii) what provisions will be taken if the participant regains the capacity to consent, (iii) who will be used as a legally authorized representative, and (iv) what provisions will be made for the assent of the participant.

The clinical staff who refer patients to the study will be asked if the patient has capacity to consent for the study. In addition, if it appears that a patient does not understand the consent procedure or does not have the capacity to consent to screening, we will not screen them for participation in the study.

Additional VA questions:

i) List the people to whom you have formally delegated responsibility to obtain informed consent, and state whether they have the appropriate training to perform this activity.

The PI, VA Co-I or qualified VA research staff have responsibility of obtaining oral assent prior to conducting the screening interview individuals for the study.

ii) Will legally effective informed consent be obtained from the participant or the participant's legally authorized representative (LAR) or both? If LAR, is it clear who can serve as LAR?

Title : Transcranial Magnetic Stimulation for the Treatment of Veterans With Alcohol Use Disorders
Approval Period: 02/28/2025 - 02/28/2026

N/A

iii) Will the circumstances of the consent process minimize the possibility of coercion or undue influence and provide the prospective participant or their representative sufficient opportunity to consider whether to participate?

Potential participants will be given information about the study and it will be made clear that participating in the screening interview is completely voluntary and choice of participation will not affect their current or future VA treatment in any manner.

iv) Will the circumstances of the consent process minimize the possibility of coercion or undue influence?

Patients screened for participation will be explicitly informed that completing the screening interview is completely voluntary and there will be no compensation for the screen. The participants are told there is no compensation for the screening interview.

v) Will the information being communicated to the participant or the representative during the consent process exclude any exculpatory language through which the participant or the representative is made to waive or appear to waive the participant's legal rights, or release or appear to release the investigator, the sponsor, the institution, or its agent from liability for negligence (e.g. I give up any property rights I may have in bodily fluids or tissue samples obtained in the course of the research)?

No.

vi) Please confirm the following:

- A witness to the participant's signature or the participant's legally authorized representative's signature will sign and date the consent document.**
- If the sponsor or the IRB requires a witness to the consenting process in addition to the witness to the participant's signature and if the same person is needed to serve both capacities, a note to that effect is placed under the witness's signature line.**
- A copy of the signed and dated consent document will be given to the person signing the consent document.**
- The consent form is on the VA Form 10-1086.**

Select ALL applicable regulatory criteria for a Waiver of Documentation and provide a protocol-specific justification:

- 1) **45 CFR 46.117(c)(1)(i), that the only record linking the participants and the research would be the consent document, and the principal risk would be potential harm resulting from a breach of confidentiality; each participant (or legally authorized representative) will be asked whether he/she wants documentation linking the participant with the research, and the participant's wishes govern.**
- 2) **Y 45 CFR 46.117(c)(1)(ii), that the research presents no more than minimal risk of harm to participants and involves no procedures for which written consent is normally required outside of the research context.**
- 3) **45 CFR 46.117(c)(1)(iii), if participants or legally authorized representatives (LAR) are members of a distinct cultural group in which signing forms is not the norm, the research presents no more than minimal risk and there is an appropriate alternative mechanism for documenting that informed consent was obtained.**
- 4) **Y 21 CFR 56.109(c)(1), presents no more than minimal risk of harm to participants and involves no procedures for which written consent is normally required outside of the research context.**

Rationale for above selection:

We believe it is an excessive and unreasonable burden on the potential participant to require those with a potential history of bipolar/cyclothymia or schizophrenia-spectrum disorders to complete the entire lengthy informed consent process to conduct this brief screen for study eligibility. Such individuals would be immediately excluded after reading through the entire consent, which would likely be highly frustrating for many potential participants. We request the IRB consider the patient population of this study and our desire to minimize any unnecessary burden on potential participants.

13.2 Consent

Informed Consent

Check if VA related **Y**

a) Describe the informed consent process. Include the following.

i) Who is obtaining consent? (The person obtaining consent must be knowledgeable about the study.)

Title : Transcranial Magnetic Stimulation for the Treatment of Veterans With Alcohol Use Disorders
Approval Period: 02/28/2025 - 02/28/2026

- ii) When and where will consent be obtained?
- iii) How much time will be devoted to consent discussion?
- iv) Will these periods provide sufficient opportunity for the participant to consider whether or not to participate and sign the written consent?
- v) What steps are you taking to minimize the possibility of coercion and undue influence?
- vi) If consent relates to children and if you have a reason for only one parent signing, provide that rationale for IRB consideration.

(i) Study personnel obtaining consent will be one of the investigators, or RA, who have been trained to give informed consents. (ii) The consenting is always done after the potential research subject has been presented with a description of the study and indicated interest in participating, and before any information is collected, or any questionnaires answered. The consenting will typically takes place in one of the private interview rooms in the VAPAHCs MIRECC Bldg 5, 4th floor or at the participants VAPAHCs Addiction Treatment Program. (iii) Sufficient time will be allowed for participants to read the consent and to ask any and all questions they may have and discuss the study with study personnel obtaining consent. We estimate this will take approximately 30 minutes. (iv) The potential participant may take the consent to review, and contact study personnel to ask further questions or sign it. (v) Participants will be told that involvement in the study is completely voluntary, and that they can withdraw at any time, for any reason. Research personnel will also emphasize that any treatment they receive at VAPAHCs will not be affected by their choice to participate in the study. (vi) n/a

b) What is the Procedure to assess understanding of the information contained in the consent? How will the information be provided to participants if they do not understand English or if they have a hearing impairment? See HRPP Chapter 12.2 for guidance.

Participants will be given an explanation of the consent form by trained research staff. In addition, they will be given ample time to read and review the consent forms and given the opportunity to ask questions or clarification. Given the nature of the study, individuals must be fluent in English and not have visual or auditory acuity impairment that would prevent them from completing the assessments, including the consent.

c) What steps are you taking to determine that potential participants have the capacity to participate in the decision-making process? If your study may enroll adults who are unable to consent, describe (i) how you will assess the capacity to consent, (ii) what provisions will be taken if the participant regains the capacity to consent, (iii) who will be used as a legally authorized representative, and (iv) what provisions will be made for the assent of the participant.

The study will not enroll individuals who are not able to give written, informed consent. If there is any question regarding the potential participant's capacity to give informed consent, they will be screened by the study PI/PD, who is a licensed clinical psychologist/neuropsychologist for the cognitive competency to provide written informed consent.

Additional VA questions:

i) List the people to whom you have formally delegated responsibility to obtain informed consent, and state whether they have the appropriate training to perform this activity.

Drs. [name], [name], [name], [name], [name], [name] and study RAs are all delegated responsible staff to obtain written informed consent. All have been trained in the study, and process for obtaining consent. To-be-hired research personnel will be trained in the consent processes and completed the required training in Human Subjects, Good Clinical Practice, and HIPAA prior to obtaining informed consent.

ii) Will legally effective informed consent be obtained from the participant or the participant's legally authorized representative (LAR) or both? If LAR, is it clear who can serve as LAR?

No. Individuals who are not able to competently provide independent written informed consent will not be included in the study.

iii) Will the circumstances of the consent process minimize the possibility of coercion or undue influence and provide the prospective participant or their representative sufficient opportunity to consider whether to participate?

Participants will be given ample time to consider participation in the study and for signing the written consent form. Participants will also be told that their involvement in the study is completely voluntary, and that they can withdraw at any time, for any reason. Study personnel obtaining informed consent will also emphasize that the treatment they receive at the VAPAHCs will not be affected by whether they decline or participate in the study.

iv) Will the circumstances of the consent process minimize the possibility of coercion or undue influence?

Title : Transcranial Magnetic Stimulation for the Treatment of Veterans With Alcohol Use Disorders
Approval Period: 02/28/2025 - 02/28/2026

Participants will be informed that participation in the study is completely voluntary, and that they can withdraw at any time, for any reason. Study personnel obtaining informed consent will also emphasize that the treatment they receive at VAPAHCS will not be affected by whether they decline or participate in the study minimizing risk of coercion. The level of participant compensation is appropriate for the population being studied and no cash or checks will be dispensed.

v) **Will the information being communicated to the participant or the representative during the consent process exclude any exculpatory language through which the participant or the representative is made to waive or appear to waive the participant's legal rights, or release or appear to release the investigator, the sponsor, the institution, or its agent from liability for negligence (e.g. I give up any property rights I may have in bodily fluids or tissue samples obtained in the course of the research)?**

No. All information presented to the participant, including documents they must sign, will be approved by the IRB.

vi) **Please confirm the following:**

- A witness to the participant's signature or the participant's legally authorized representative's signature will sign and date the consent document.**
- If the sponsor or the IRB requires a witness to the consenting process in addition to the witness to the participant's signature and if the same person is needed to serve both capacities, a note to that effect is placed under the witness's signature line.**
- A copy of the signed and dated consent document will be given to the person signing the consent document.**
- The consent form is on the VA Form 10-1086.**

14. Assent Background (less than 18 years of age)

15. HIPAA Background

15.1 Authorization

va hippa

15.2 Waiver of Authorization for

waiver of authorization for recruitment

Recruitment

a) **Describe the protected health information (PHI) needed to conduct screening or recruitment. PHI is health information linked to HIPAA identifiers. List BOTH health information AND HIPAA identifiers. If you are using STARR, use the Data Privacy Attestation to ensure that your request will match your IRB-approved protocol.**

Name, last 4 of SSN, age, date of birth, sex, telephone number (for contact about eligibility), medical, specific psychiatric history regarding bipolar/manic and schizophrenia-spectrum symptoms. • We believe it is an excessive burden on the potential participant to require them to complete the entire lengthy informed consent to conduct this brief screen for study eligibility. The rTMS treatment parameters proposed in this study have been associated with increased risk for a manic symptoms in those with bipolar disorder and cyclothymia. Although the research on schizophrenia-spectrum disorders is equivocal, exacerbation of psychotic symptoms have been reported with the rTMS treatment parameters proposed in this study. Qualified research personnel will conduct this screen specifically to determine basic eligibility for the study. The screen is will be 15-20 minutes in duration. • The purpose of the screening interview is given in the script preceding screening. Participant oral assent will be confirmed prior to screening. VA waiver of HIPAA authorization for recruitment has also been included in the protocol. • Potential participants will be given information about the study and it will be made clear that participating in the screening interview is completely voluntary, they will not be compensated for the screening interview, and choice of participation will not affect their current or future VA treatment in any manner.

b) Please Answer:

Title : Transcranial Magnetic Stimulation for the Treatment of Veterans With Alcohol Use Disorders
Approval Period: 02/28/2025 - 02/28/2026

Y Do you certify that the use or disclosure of protected health information involves no more than a minimal risk to the privacy of individuals?

Y Do you certify that the research could not practically be conducted without the waiver?

All data including signed consent form documents must be retained for a minimum of three years past the completion of the research. Additional requirements may be imposed by your funding agency, your department, or other entities. (Policy on Retention of and Access to Research Data, Research Policy Handbook, <http://doeresearch.stanford.edu/policies/research-policy-handbook/conduct-research/retention-and-access-research-data>)

APPROVAL LETTER/NOTICE NOTE: List all items (verbatim) that you want to be included in your approval letter (e.g., Amendment date, Investigator's Brochure version, consent form(s) version(s), advertisement name, etc.) in the box below.

Y By checking this box, I verify that I, as the Protocol Director (PD) responsible for this research protocol, have read and agree to abide by the above obligations, or that I have been delegated authority by the PD to certify that the PD has read and agrees to abide by the above obligations.

Data Analyses

Primary Hypothesis:

1a) Veterans who receive active rTMS treatment for AUD demonstrate a significantly lower frequency of relapse at 6 months following treatment than controls (i.e., Veterans with AUD who receive sham rTMS).

Statistical Approach: Primary Hypothesis 1a will be tested with binary logistic regression. The criterion/dependent measure is relapse status (abstained or relapsed during the 6 months after last rTMS session). Treatment group (active rTMS vs. control) is the target predictor, and covariates will include age and composite neurocognitive functioning (based on demographically adjusted RBANS total score) as these variables may account for both within and between subject group variance [89, 91]. PTSD severity (based on PCL-5 total score), substance use severity (based on NIDA Drug Survey composite score), depression severity (based on BDI total score), and/or smoking severity (based on pack-years) will be considered as covariates if, after random assignment, there are post-hoc differences between treatment groups on these variables following breaking of the blind.

1b) Veterans who receive active rTMS treatment for AUD will demonstrate a significantly greater duration of abstinence in the 6 months following treatment than controls.

Statistical Approach: Primary Hypothesis 1b will be tested with Cox regression. The criterion/dependent measure is duration of abstinence after final rTMS session, and covariates include those listed for Primary Hypothesis 1a.

Secondary Hypothesis:

In the active rTMS group, Veterans with: (a) lower Glx concentration, (b) lower perfusion (blood flow), and (c) smaller volume of the left DLPFC at baseline will demonstrate a longer duration of abstinence over 6 months post treatment. Confirmation of this hypothesis will indicate that participants who exhibit lower baseline Glx concentration, lower perfusion (blood flow), and/or smaller left DLPFC volume, and receive active rTMS, demonstrate the most robust rTMS treatment response because rTMS addresses these key neurobiological deficits that are associated with increased relapse risk. Confirmation of this hypothesis will advance our understanding of the neurobiological characteristics that predict the greatest benefit from rTMS at entry into treatment for AUD.

Statistical Approach: The Secondary Hypothesis will be tested with generalized linear mixed modeling or linear mixed modeling, depending on the distribution of the dependent measure. Duration of abstinence is the dependent measure. Neuroimaging measure (e.g., Glx level) and treatment group (active rTMS vs. control) are the target predictors, with age as a covariate because it will likely account for significant within and between subject variance [20]. Smoking, PTSD and/or substance use severities will be used as covariates if there are post-hoc differences between treatment groups on these variables after random assignment. We predict an interaction between the specific neuroimaging measure (e.g., Glx level) and treatment group; follow-up simple effect tests will indicate that participants in the active rTMS group with lower Glx concentration, lower perfusion (blood flow), and smaller volume of the left DLPFC at baseline will show the longest duration of abstinence. Separate models will be run for each neuroimaging predictor to minimize the risk of overfitting and corresponding inflated Type I error. To control significance levels of main effects and interactions for multiplicity of tests, we will employ a modified Bonferroni procedure described in our previous studies (see [71] for details).

Exploratory Hypothesis 1

1a) Veterans with co-occurring MDD, who receive active rTMS, demonstrate a significantly lower frequency of relapse over 6 months following treatment than controls (i.e. Veterans with co-occurring MDD who receive sham rTMS).

Statistical Approach: Exploratory Hypothesis 1a will be tested with binary logistic regression. The criterion/dependent measure is relapse status (abstained or relapsed during the 6 months after last rTMS session). Treatment group (active rTMS vs. control) is the target predictor, with antidepressant use (binary, yes/no) as a covariate. Education and severity of PTSD, substance use, and/or depressive symptomatology will be considered as covariates if, after random assignment, there are post-hoc differences between treatment groups on these variables following breaking of the blind.

1b) Veterans with co-occurring MDD, who receive active rTMS, demonstrate significantly greater duration of abstinence in the 6 months following treatment than controls.

Statistical Approach: Exploratory Hypothesis 1b will be tested with Cox regression. The criterion/dependent measure is duration of abstinence after the final rTMS session. The target predictor and covariates include those for Exploratory Hypothesis 1a.

Exploratory Hypothesis 2

2a) Cigarette smokers, who receive active rTMS, demonstrate a significantly lower frequency of relapse over 6 months following treatment than controls (i.e., Veterans with co-occurring smoking who receive sham rTMS).

Statistical Approach: Exploratory Hypothesis 2a will be tested with binary logistic regression. The criterion/dependent measure is relapse status (abstained or relapsed during the 6 months after last rTMS session). Treatment group (active rTMS vs. control) is the target predictor and with current pharmacotherapy for smoking cessation use (binary, yes/no) as a covariate. Education and severity of PTSD, substance use, and/or smoking severity (based on pack-years) will be considered as covariates if, after random assignment, there are post-hoc differences between treatment groups on these variables following breaking of the blind.

2b) Smokers, who receive active rTMS, demonstrate a significantly greater duration of abstinence over the 6 months following psychosocial treatment than controls.

Statistical Approach: Exploratory Hypothesis 2b will be tested with Cox regression. The criterion/dependent measure is duration of abstinence after final rTMS session. Treatment group is the target predictor and covariates include those for Exploratory Hypothesis 2a.

Tertiary Analyses

We will concurrently examine the associations between treatment group, multiple neurobiological, neurocognitive and clinical variables (and their potential interactions) and relapse status via an advanced multivariate dynamic longitudinal latent variable modeling framework [23]. However, we are mindful of the proposed sample size and will avoid building models that risk overparameterization and overfitting.

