Participants will not be compensated for study screening. Participants will receive a maximum of \$240 for all baseline and treatment phase and week 5 follow-up study procedures. If participants do not complete all baseline or post-treatment visit procedures, they will receive a pro-rated amount that is lower than \$200, based on how many procedures you completed. Participants will receive an additional \$50 if all monthly contact from week 9 – 25 are completed. Total possible compensation over 1 year is approximately \$290. The mechanism of payment will adhere to the VA mandated procedure: payment form, which the participant can obtain cash or check at the VA Palo Alto upon completion of Baseline and Post-treatment Visit. This rate of compensation is commensurate with other AUD research being conducted at the VAPAHCS and the payment mechanism is used by other alcohol/substance abuse research currently conducted at the VA Palo Alto. The total amount of payment is proportional to the participant's time and effort and is intended to facilitate participation without adding undue influence.

l) Costs. Please explain any costs that will be charged to the participant.

No costs will be incurred by any participant.

m) Estimate the probable duration of the entire study. Also estimate the total time per participant for: (i) screening of participant; (ii) active participation in study; (iii) analysis of participant data.

(i) Probable duration of study = 7 years. End date is 30 September 24. Participant recruitment will likely end 30 September 23. Final fiscal year 2024 will be devoted to data processing and analyses.

(ii) Total time per participant:

Study Phase	Estimated Participation Time
Screening:	20-30 min
Baseline:	6.5 hours, 2-4 hours/day over 1 week.
Treatment:	6.5 hours, 40 min/day, over 2 weeks
Follow-up:	Week 5, 4 hours typically over 2 days

Title : Transcranial Magnetic Stimulation for the Treatment of Veterans With Alcohol Use Disorders
Approval Period: 02/28/2025 - 02/28/2026

Follow-up Weeks 9 – 61: 4 hours

Total Active Participation Time = approx. 22 hours over 1 year.

All procedures will be conducted before or after normal ATS clinic hours, or during lunch break, to not interfere with the patient's treatment schedule. The project will be conducted at the VAPAHCS MIRECC Palo Alto Division, which is on the same campus as the FOR program.

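### Hypothesis 1a has no rule for participants lost while abstinent, and the follow-up bonus ends before the contact that establishes 6-month status

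*Combined protocol and SAP*

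**What the plan says.** Under Data Analyses, the first primary hypothesis compares relapse frequency at 6 months between active and sham: "Primary Hypothesis 1a will be tested with binary logistic regression". The outcome is "relapse status (abstained or relapsed during the 6 months after last rTMS session"), adjusted for age and a neurocognitive score, with further covariates if the arms differ. The section says nothing about missing outcomes, imputation, the analysis population or how a lost participant is classified. The companion hypothesis concerns duration of abstinence: "Primary Hypothesis 1b will be tested with Cox regression".

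Status comes from monthly contacts for a year after treatment, each covering the previous 30 days (section 2a, Monthly Follow-ups). Section 8k pays a maximum of $240 for the baseline, treatment and week 5 procedures, and a further $50 "if all monthly contact from week 9 – 25 are completed", about $290 in all. Section 8m continues the contacts well beyond that: "Follow-up Weeks 9 – 61: 4 hours". It places the post-treatment visit at "Week 5, 4 hours typically over 2 days", and section 2a puts that visit 3 to 4 days after treatment ends.

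**The concern.** One report of relapse settles a participant's 6-month status, whatever happens afterwards. Abstinence is settled only by a contact that reaches the end of the window. So someone who relapses and then disappears can be classified, while someone who disappears while abstinent cannot. With no rule given, standard software fits a logistic model to those with an observed outcome, and the excluded group is then selected on the outcome even if dropout has nothing to do with relapse.

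The payment schedule could add to this, because the completion bonus stops before the contact that would confirm abstinence. At stake are the 6-month relapse frequencies that 1a is about, the treatment comparison if the arms lose participants unequally, and usable numbers in a trial of 50 per arm. Further, if the rule is chosen after the blind is broken, it becomes another discretionary choice alongside the covariates already deferred to that point.

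**Working it through.** **Payment and timeline.** The plan's total reproduces: 240 + 50 = 290. No payment is therefore attached to contacts after week 25.

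- At 4-week spacing the paid contacts are weeks 9, 13, 17, 21 and 25; the next are weeks 29 and 33.
- A post-treatment visit at week 5, 3 to 4 days after the last session, puts that session at about week 4 to 5. Week 25 is then 20 to 21 weeks later (4.6 to 4.8 months), and 6 months (26 weeks) falls at week 30 to 31.
- Week 0 is undefined. With the last session as early as week 2, week 25 is 23 weeks later (5.3 months) and 6 months falls at week 28.
- The first contact at or after 6 months is thus week 29 or week 33, depending on how weeks and months are counted. Neither is paid.
- Week 25 reaches 6 months only if weeks run from the last session itself and a month is 4 weeks (24 weeks). The week 5 visit contradicts that count.

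**Inputs for the bias.** Section 1b gives at least 60% relapse within 6 months, used here as the sham rate. The 40% active rate and all loss rates are assumptions; the plan states no effect size or dropout rate.

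**Loss unrelated to relapse.** Take constant hazards over the window, with true relapse p, loss d, l = −ln(1−p) and m = −ln(1−d).

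- Relapse seen: R = l/(l+m) × [1 − exp(−(l+m))]
- Abstinent and retained: A = (1−p)(1−d)
- Frequency among those with known status: R/(R+A)

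25% loss in both arms:

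- Sham: A = 0.4 × 0.75 = 0.300, R = 0.533, giving 0.533/0.833 = 64.0%.
- Active: A = 0.6 × 0.75 = 0.450, R = 0.352, giving 0.352/0.802 = 43.9%.
- Participants with known status: 50 × (0.833 + 0.802), about 82 of 100.
- Odds ratio 0.440; true value (0.4/0.6)/(0.6/0.4) = 0.444.

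Over 10% to 40% equal loss, the frequencies run from 61.5% v 41.4% to 67.0% v 47.1%, and the odds ratio from 0.443 to 0.437.

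Unequal loss:

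| True relapse, sham v active | Loss, sham v active | Observed relapse | Result |
|---|---|---|---|
| 60% v 60% | 30% v 10% | 64.9% v 61.5% | OR 0.86; rejection probability 0.063 at two-sided 0.05 |
| 60% v 60% | 40% v 10% | 67.0% v 61.5% | OR 0.78; rejection probability 0.082 |
| 60% v 40% | 30% v 10% | 64.9% v 41.4% | 23.5 points, not 20 |
| 60% v 40% | 10% v 30% | 61.5% v 44.8% | 16.6 points, not 20 |

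The rejection probabilities use a pooled two-proportion z test on the expected numbers with known status.

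**Loss only after the bonus ends.** If 20% of those still abstinent at week 25 miss the confirming contact, A = 0.8 × (1−p), and the observed frequencies are about 64.5% and 44.6%.

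**Relapsers who vanish silently.** Suppose 20% of relapsers are lost unreported and nobody else is lost.

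- Known status only: 0.48/(0.48 + 0.40) = 54.5% and 0.32/(0.32 + 0.60) = 34.8%, both too low.
- Censored at last contact (relapse hazard cut by 20%): 1 − 0.4^0.8 = 52.0% and 1 − 0.6^0.8 = 33.5%, lower still.
- Lost counted as relapsed: 60% and 40%, correct here.

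**Both kinds of loss.** Add 15% unrelated loss to the 20% silent relapse. Censoring still gives 52.0% and 33.5%. Counting the lost as relapsed gives 1 − 0.4 × 0.85 = 66% and 1 − 0.6 × 0.85 = 49%. The true 60% and 40% lie between the two.

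**The case against.** The plan never says that lost participants are excluded. A reader might infer that it prescribes a complete-case analysis, but it names only a model and an outcome. Counting the lost as relapsed, or imputing them, would fit the same words. The grant application, which is not in hand, may say more. This stands: the defect is an unspecified rule, and the complete-case figures show what follows if nothing is added.

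A reader might also infer that the reported frequencies must be too high and the treatment effect must be biased. Neither follows. The direction depends on why people are lost, and silent relapse reverses it. With equal, unrelated loss the odds ratio is almost unchanged. Even the 30% v 10% null case raises the rejection probability only to about 0.06, and no document supports a 20-point gap in loss.

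Censoring is not a full cure, and a discrete-time model on monthly contacts comes close to repeating the Cox analysis in 1b. Both points stand, which is why censoring should not be the only estimate. But 1b does not settle 1a. They are separate primary hypotheses, and 1a as written has no means of using partial follow-up.

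Finally, contacts continue unpaid to week 61, so the week 25 limit does not mean that 6-month status goes uncollected, and nothing in the documents measures what $50 does for retention. By the plan's own dates (recruitment ending in 2023, study end 30 September 2024) most or all of the 6-month contacts may be past. The bonus change therefore matters only for contacts that remain.

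**Conclusion.** The point holds in limited form and should be acted on. Hypothesis 1a lacks a rule for participants lost while abstinent, and its default analysis selects on the outcome. If loss is unrelated to relapse, the 6-month frequencies are overstated by about 1.4 to 7 points at 10% to 40% loss. The treatment comparison is distorted when loss differs by arm, modestly in the cases examined. If relapsers leave silently, the frequencies are understated instead. These sizes rest on constant hazards, an assumed 40% active rate and assumed loss rates. The documents do not support reading this as a certain bias in favour of active treatment.

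The timing finding is firmer. On every week count consistent with the week 5 visit, the bonus stops short of 6 months.

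**What to change.** 1. **Bonus.** For any contacts still to come, extend the existing completion bonus through the first contact at or after 6 months from the last session (week 29 to 33), and define week 0 so that this contact is fixed. The cost is at most a small added payment per participant.

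2. **Analysis.** Before unblinding, keep 1a as a 6-month relapse comparison, but estimate relapse by arm, and the difference, from the monthly data. Censor lost participants at last contact, for example in a discrete-time (complementary log-log) model with the 1a covariates. Beside it, report the analysis that counts the lost as relapsed, and give the number and timing of losses by arm. No new data are needed. The costs are overlap with 1b and reliance on non-informative loss in the first estimate. The second has its own weakness: in the 30% v 10% null case it gives 1 − 0.4 × 0.7 = 72% v 1 − 0.4 × 0.9 = 64%. The two should therefore be read together. Section 8m places the breaking of the blind in year 6; if that has happened, label the change as made after unblinding.
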